So far, recent immune-modulatory therapies decrease MS relapse rate and disease severity¹⁶ but they do not slow the disease process. Because such therapies, unfortunately, do not affect accumulation of MS disabilities and comorbidities and because at least some MS related impairments are inactivity related rather than a result of non-reversible tissue injury, exercise rehabilitation therapy has become an important part of overall MS treatment. Indeed, a multitude of low to moderate intensity **exercise intervention studies in MS** already reported small (+10-15%) but significant improvements in muscle strength and exercise capacity³. Surprisingly however, **effects are lower compared to healthy controls and some other disease populations**. In an attempt to further improve rehabilitation outcome we therefore recently performed higher intensity training (HIT) studies in an animal MS model (Experimental Autoimmune Encephalomyelitis, EAE¹⁷) and in MS patients¹⁸. Although results are promising with substantially improved (+25-30%) muscle strength and exercise capacity following 8-12w of exercise^{17, 18} most MS subjects reported **higher post exercise muscle fatigue and overall perceived exertion rates (BORG: 14.7±1.5 vs. 12.7±1.3)** compared to low-to-moderate intensity training¹⁵.

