Figure 1. Serum lactate concentrations (means \pm SE's) during submaximal (two 6-min exercise bouts [25% of W_{max}]) and maximal graded exercise testing (cycling) in healthy controls (HC, $n=17$) and multiple sclerosis (MS, $n=20$) patients (Pilot data taken from [name] & [name] et al. Increased exercise-induced lactate accumulation in MS. Manuscript in preparation).

Muscle carnosine loading

Carnosine (β -alanyl-L-histidine) is found in high concentrations in mammalian skeletal muscle^{28, 29}. Its **physiological role** is related to **(I) contractile function** in general and more specific to Ca^{++} handling²⁹. In addition, **(II)** carnosine has also been shown to **buffer muscle pH** resulting from exercise-induced acidosis²⁹ and it has been suggested to **affect mitochondrial respiration**³⁰ and to **protect against exercise-induced oxidative stress**³¹. Here, carnosine reduces the production of thiobarbituric acid reactive substances and malondialdehyde due to lipid peroxidation^{28, 29}. **High (or elevated) muscle carnosine content may thus be advantageous to improve muscle contractile properties and/or myocellular energy supply during exercise intervention.** Because skeletal muscle carnosine synthesis is mainly determined by β -alanine availability³², exogenous (dietary, 2-6g/d, 4-10w) intake of β -alanine has been successfully applied to increase muscle carnosine content (+80%, **carnosine loading**) in various rodent disease models³³⁻³⁵ and healthy volunteers³⁶⁻³⁸. In untrained and aged subjects β -alanine supplementation has recently been shown to specifically improve maximal power output (+13-30%) in exercise types lasting 1-4min³⁹. Interestingly, trained muscles load more efficiently with carnosine than untrained muscles⁴⁰. Consequently, β -alanine is rapidly becoming a popular **ergogenic substance** in the (clinical) exercise/sports community.

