Figure 4. Muscle carnosine concentrations (mmol/kg WW) in EAE rats (animal MS model), without (EAE CON, n=13) and with carnosine (EAE CA, n=13) or β -alanine (EAE BA, n=13) supplementation. *p<0.05 compared to control group.

Research objectives

Increasing evidence favours exercise therapy as an efficient tool to counteract inactivity related secondary symptoms in MS. Furthermore, exercise therapy may affect MS-associated muscle contractile and energy supply dysfunctions. So far, low to moderate intensity exercise rehabilitation has shown to induce small but consistent improvements in several functional parameters. High intensity exercise training in MS seems to further improve this. However, although results are promising, impairments in both muscle contraction and energy supply probably attenuate therapy outcome. In keeping with the above described physiological role of skeletal muscle carnosine and because muscle carnosine content may be lower in MS, **the primary aim of the present project is to investigate whether carnosine loading improves exercise therapy outcome (exercise capacity, body composition) and performance in MS.** If the latter hypothesis can be confirmed, muscle carnosine loading could be a novel intervention to improve exercise capacity and muscle function in this population.

Ergogenic potential of muscle carnosine loading and exercise therapy in MS

So far, it is clear that β -alanine intake enhances exercise capacity of untrained, trained and aged individuals by improving contractile properties, maintaining higher intracellular energy levels and optimizing training adaptations. Because early fatigue of contracting musculature during rehabilitation is the predominant cause of exercise cessation, postponing exercise-induced fatigue by β -alanine supplementation will be clinically very relevant (improving exercise therapy efficiency). Consequently, we aim to research the ergogenic potential of β -alanine intake in MS rehabilitation and **hypothesize that β -alanine supplementation in combination with exercise therapy optimizes therapy outcome (exercise capacity, body composition) and performance in this population.**

METHODS

Subjects

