The supplementation protocol of β -alanine (Etixx $^{\circledR}$ Omega Pharma Belgium NV) involves oral intake of 4 x 800mg (3.2g/day^{29, 43}) daily with at least 2h apart of slow-release β -alanine during the first 12 weeks. After this loading period, subjects will receive a maintenance dose of 2 x 800mg (1.6g/day) β -alanine for the remaining study duration. Placebo groups will follow the same supplementation protocol with placebo tablets that will have identical taste and appearance. All subjects will be advised to take the tablets together with meals. This supplement is frequently used to improve sport performances in athletes. The beta-alanine supplement consists of beta-alanine, hydroxymethylcellulose, cellulose, silicon dioxide, magnesium stearate and zinc. In some cases, taking beta-alanine can provoke a tingling feel (paresthesia) on the skin which is reversible within the hour. However, this is not dangerous and completely reversible. To prevent this paresthesia, β -alanine tablets will consist of slow-release β -alanine which, together with the spread intake throughout the day, will not provoke this discomfort.

Measurements

Exercise capacity & serum lactate. Exercise capacity will be assessed using a maximal (12-lead ECG) graded cardiopulmonary exercise test (♂: 30W+15W/min, ♀: 20W+10W/min) with pulmonary gas exchange analysis (Jaeger Oxycon®). Subjects will perform the exercise test on their personal bicycle (Cyclos2® Leipzig, Germany). VO₂, VE, RER will be monitored and 2min capillary blood samples will be obtained to analyse blood lactate concentrations (Analox®) and determine the anaerobic threshold before, during and after exercise. RER values will be evaluated to verify if the test was performed maximally (RER >1.1).

Body composition Whole body fat and lean tissue mass will be obtained using Dual Energy X-ray Absorptiometry scan (DEXA) (Hologic Series Delphi-A Fan Beam X-ray Bone Densitometer, Vilvoorde, Belgium). A calibrated analogue weight scale (Seca®) will be used to measure total body mass.

Statistical analysis

Baseline differences between groups and post-intervention differences will be analysed using an unpaired student's t-test and a 4x2 ANOVA for repeated measures, respectively (SAS Institute®). The threshold for statistical significance will be set at p<0.05.

Reference List

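### The primary aim spans exercise capacity, body composition and an undefined performance outcome, but no primary variable, β-alanine contrast or success rule is named, so the error rate of its conclusion is not fixed

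*Combined protocol and SAP*

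**What the plan says.** Under Research objectives, the primary aim is to find out "whether carnosine loading improves exercise therapy outcome (exercise capacity, body composition) and performance in MS". The next subsection repeats the same set as the hypothesis, that β-alanine "in combination with exercise therapy optimizes therapy outcome (exercise capacity, body composition) and performance in this population". The protocol treats this as something that can be decided: "If the latter hypothesis can be confirmed, muscle carnosine loading could be a novel intervention".

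Under Measurements, the graded exercise test yields VO₂, VE, RER, blood lactate and the anaerobic threshold. RER has a stated checking role: "RER values will be evaluated to verify if the test was performed maximally". Body composition is fat mass and lean mass by DEXA, plus total body mass. Trunk strength, listed under Study design, is measured for core stability. No variable is called primary, and no measurement is tied to the word performance.

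The Statistical analysis section has two sentences. Baseline differences get an unpaired t-test, post-intervention differences get "a 4x2 ANOVA for repeated measures", and "The threshold for statistical significance will be set at p<0.05". Sidedness, the decisive ANOVA effect, a β-alanine contrast, a rule for combining outcomes and any multiplicity adjustment are not stated.

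**The concern.** One hypothesis is to be confirmed or not, yet several variables could bear on it, each at 0.05. The plan does not say whether one favourable variable is enough or every domain must succeed. Nor does it say whether MS β-alanine is compared with MS placebo directly or only after a significant group-by-time F test. Those rules set the false-positive rate of the main conclusion. While they are unwritten, the rate is undetermined and the rules remain open to choice after results are known.

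The one test the plan does name does not answer the primary question by itself. A group-by-time test across four groups asks whether any of the four mean changes differ. A difference in training response between MS and healthy controls (HC) can make it significant without any β-alanine effect.

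**Working it through.** **The plan's own figure.** The only error-rate figure is 0.05. No power, SD, effect size or family-wise rate is given, so there is no derived figure to reproduce.

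**Inputs from the protocol.** Four groups of 10; PRE and POST measurements; threshold 0.05. With two time points, the group-by-time test equals a one-way ANOVA on change, F(3, 36).

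**Assumptions not in the protocol.** No β-alanine effect; normally distributed changes; equal correlations ρ between variables, from 0.7 to 0; two-sided tests; each variable coded so that positive is favourable. The count k is a matter of reading: four (VO₂, anaerobic threshold, fat mass, lean mass), or seven on a broad count that adds VE, lactate and body mass. RER and trunk strength are left out.

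**Step 1: direct test of MS β-alanine against MS placebo, any one variable counts.** A two-sided 0.05 test gives a false favourable result with probability 0.025. At ρ = 0 the chance of at least one is 1 − 0.975^k:
- k = 4: 1 − 0.975⁴ = 0.096
- k = 7: 1 − 0.975⁷ = 0.162

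At ρ = 0.7, integrating the normal model gives 0.065 (k = 4) and 0.089 (k = 7). Simulated two-group t-tests with 10 per group give 0.067 and 0.091.

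**Step 2: the same contrast, counted only after a significant F(3, 36).** Simulated, with MS and HC responding equally to training. Ranges run from ρ = 0.7 to 0 and cover both a two-group and a pooled error term:
- k = 1: 0.009-0.010
- k = 4: 0.027-0.039
- k = 7: 0.040-0.066

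**Step 3: is the F test specific to β-alanine?** Let HC change exceed MS change by d SDs of the change, with no β-alanine effect. The noncentrality is 10 × 4 × (d/2)² = 10d². The value of d is purely an assumption.
- d = 0.5: noncentrality 2.5, probability that F is significant 0.21
- d = 1: noncentrality 10, probability 0.71

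**Step 4: all domains must succeed.** If at least one domain has no effect, the joint success probability cannot exceed that domain's own: 0.05 two-sided, 0.025 in the favourable direction. It is far lower only when no domain has an effect. For three domains it is then 0.025³ = 0.000016 at ρ = 0 and about 0.004 at ρ = 0.7.

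| Rule | One variable | Four | Seven |
|---|---|---|---|
| Any one counts, direct test | 2.5% | 6.5-10% | 9-16% |
| Any one counts, after F, equal training response | about 1% | 3-4% | 4-6.5% |
| All must succeed (favourable direction) | 2.5% | at most 2.5% | at most 2.5% |

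**The case against.** The strongest defence is that the plan does assign post-intervention differences to the ANOVA, and that the aim is limited to MS, so the MS β-alanine against MS placebo contrast can be inferred. With the F test as a gate and equal training response, four variables give only 3-4%. This is also a 40-person study whose stated consequence is modest. Part of this stands: the natural contrast is easy to guess, and inflation under a strict gate is small for four variables. But the plan does not state the gate, and its protection depends on MS and HC training alike.

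Several stronger readings are tempting, and the documents do not support them:
- **That performance is not measured.** The graded cycling test or the trunk-strength test might be meant. The word is undefined, which is a different fault.
- **That the protocol shows MS will respond less in this trial.** The statement that "effects are lower compared to healthy controls and some other disease populations" follows a sentence on low to moderate intensity training and concerns strength and exercise capacity. The same paragraph reports larger gains at higher intensity, and this trial trains at moderate to high intensity. The 0.5 and 1 SD differences are therefore hypothetical.
- **That the 9-16% figure is the trial's error rate.** VE is only monitored, the Measurements heading lists lactate beside exercise capacity, and fat, lean and total mass are structurally linked. Seven is a generous count.
- **That the protocol's evidence points to peak power.** β-alanine "has recently been shown to specifically improve maximal power output" only in efforts of 1-4 minutes, according to that sentence. After 4 minutes the graded test has reached 30 + 4 × 15 = 90 W in men and 20 + 4 × 10 = 60 W in women, and it continues to maximum.
- **That the rules will be chosen after the results are seen.** The text leaves that possible but does not show it.

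**Conclusion.** The point holds as an undetermined error rate; inflation is not established under every reading. The plan sets a hypothesis to be confirmed and gives no variable, contrast or rule by which to confirm it.

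If any one variable may count, 0.05 per test does not control the error of the conclusion. The false favourable rate is about 6.5-10% for four variables, or 9-16% for seven, where one variable would give 2.5%. Behind an F test with equal training response it is 3-4% or 4-6.5%, where one variable would give about 1%. If all domains must succeed, it is at most 2.5% in the favourable direction. A reader might infer that this last rule is always far stricter, but that holds only when no domain has any effect.

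The count of variables, the correlations, the sidedness and any MS-HC difference are assumptions. The missing rules and the F test's lack of specificity to β-alanine do not depend on them. This should be put right; it does not invalidate the design.

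**What to change.** Before any data are seen:
- Name one primary variable from the existing graded exercise test, for example peak VO₂.
- Tie it to one primary contrast: the PRE-POST change in MS β-alanine against MS placebo, two-sided at 0.05, tested directly and not conditional on the four-group F test.
- Make all other variables and the HC comparisons secondary or exploratory, reported as estimates with 95% confidence intervals.
- Define performance as the primary variable, or take the word out of the primary aim.

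If body composition must stay primary, name one variable for it and state the rule. Either both must succeed at 0.05 each, or either may at 0.025 each. The second rule has a two-sided error of 1 − 0.975² = 0.049 at ρ = 0, falling to 0.043 at ρ = 0.7.

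The change is to wording only and adds no visit or measurement. The price is a narrower primary objective: body composition is in the current aim, and secondary results alone could no longer confirm the hypothesis.
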